2.3.2 Overall risks

Monoclonal antibodies directed against immune checkpoint proteins, such as PD-L1, aim to boost endogenous immune responses directed against tumour cells. By stimulating the immune system, however, there is the potential for adverse effects on normal tissues.

Most adverse drug reactions seen with the immune checkpoint inhibitor class of agents are thought to be due to the effects of inflammatory cells on specific tissues. These risks are generally events with a potential inflammatory or immune-mediated mechanism and that may require more frequent monitoring and/or unique interventions such as immunosuppressants and/or endocrine therapy. These immune-mediated effects can occur in nearly any organ system, and are most commonly seen as gastrointestinal (GI) AEs such as colitis and diarrhoea, pneumonitis/interstitial lung disease (ILD), hepatic AEs such as liver enzyme elevations, skin events such as rash and dermatitis, and endocrinopathies including hypo- and hyper-thyroidism.

2.3.2.1 Durvalumab (MEDI4736) risks

Risks with durvalumab (MEDI4736) include, but are not limited to, diarrhoea/colitis, pneumonitis/ILD, endocrinopathies (i.e., events of hypophysitis/hypopituitarism, adrenal insufficiency, hyper- and hypo-thyroidism, type I diabetes mellitus [DM] and diabetes insipidus), hepatitis/increases in transaminases, nephritis/increases in creatinine, rash/dermatitis (including pemphigoid), myocarditis, myositis/polymyositis, immune thrombocytopenia, infusion related reactions, hypersensitivity reactions, pancreatitis, serious infections, and other rare or less frequent inflammatory events including neuromuscular toxicities (eg, Guillain-Barre syndrome, myasthenia gravis).

For information on all identified and potential risks with durvalumab (MEDI4736), please always refer to the current version of the durvalumab (MEDI4736) IB.

In the PACIFIC Study ([Antonia et al 2017](#)), treatment-emergent adverse events (TEAEs) occurred in 67.8% of patients in the durvalumab (MEDI4736) group compared to 53.4% in the placebo group. Grade 3 or 4 AEs occurred in 29.9% of patients who received durvalumab (MEDI4736) and 26.1% of those who received placebo. The most common Grade 3 or 4 AE was pneumonia, which occurred in 4.4% of patients who received durvalumab (MEDI4736) and in 3.8% of patients in the placebo group. Pneumonitis or radiation pneumonitis of any grade occurred in 33.9% and 24.8% of patients who received durvalumab (MEDI4736) and placebo, respectively; pneumonitis or radiation pneumonitis of Grade 3 or 4 occurred in 3.4% and 2.6% of patients, respectively. The most frequent AEs leading to discontinuation of durvalumab (MEDI4736) and placebo were pneumonitis or radiation pneumonitis (in 6.3% and 4.3% of patients, respectively) and pneumonia (in 1.1% and 1.3% of patients, respectively). Adverse events of special interest (AESIs) of any grade were reported in 66.1% of patients in the durvalumab (MEDI4736) group and in 48.7% of patients in the placebo group; events of Grade 3 or higher were less than 10% in both groups. The most frequent AESIs of any grade with durvalumab (MEDI4736) versus placebo were diarrhoea (18.3% and 18.8%), pneumonitis (12.6% and 7.7%), rash (12.2% and 7.3%), and pruritus (12.2% and 4.7%). Finally, the rate of imAEs was 24.2% with durvalumab (MEDI4736) and 8.1% with placebo. The rates of severe imAEs, and of pneumonitis in particular, were not significantly different (any Grade 3 or 4 immune-mediated event 3.4% and 2.6%, and Grade 3 or 4 pneumonitis 1.7% and 2.6%, for durvalumab and placebo, respectively). Overall, the safety profile of durvalumab (MEDI4736) in this population was consistent with that of other immunotherapies and with its known safety profile as monotherapy with NSCLC.

In monotherapy clinical studies, AEs at an incidence of $\geq 20\%$ include events such as fatigue and decreased appetite. Approximately 10% of patients discontinued the drug due to an AE. Please see the current version of the IB for a detailed summary of the monotherapy data including AEs, serious adverse events (SAEs), and Common Toxicity Criteria (CTC) Grades 3 to 5 events reported across the durvalumab (MEDI4736) program.

The majority of TRAEs were manageable, with dose delays, symptomatic treatment, and in the case of events suspected to have an immune basis, the use of established treatment guidelines for immune-mediated toxicity (see Section 8.4.5).

A detailed summary of durvalumab (MEDI4736) monotherapy AE data can be found in the current version of the durvalumab (MEDI4736) IB.

2.3.3 Overall benefit/risk

In summary, the potential for clinical benefit associated with inhibition of the PD-1/PD-L1 pathway, supported by the clinical benefit in terms of PFS and ORR observed in earlier studies in patients with NSCLC, including the pivotal Phase III PACIFIC Study, outweighs the known and potential risks based on the AEs reported in patients treated with durvalumab (MEDI4736) and other PD-1/PD-L1 inhibitors. Thus, the benefit/risk assessment, favours the conduct of this proposed study.

3 OBJECTIVES AND ENDPOINTS

The study objectives and corresponding endpoints/variables are listed in [Table 3](#).

Table 3 Study objectives

| OBJECTIVE | ENDPOINT/VARIABLE |
|--|--|
| PRIMARY OBJECTIVE | |
| To assess the safety and tolerability profile of durvalumab (MEDI4736) as defined by Grade 3 and Grade 4 TRAEs ^a within 6 months from the initiation of durvalumab (MEDI4736) treatment | Grade 3 or Grade 4 TRAEs ^a |
| SECONDARY OBJECTIVES | |
| Efficacy objectives | |
| To assess the efficacy of durvalumab (MEDI4736) treatment in terms of PFS and OS | Median PFS according to RECIST 1.1 as assessed by the Investigator |
| | Median PFS12 and PFS24 according to RECIST 1.1 as assessed by the Investigator |
| | Median OS, OS12, OS24, and OS36 |
| To further assess the efficacy of durvalumab (MEDI4736) treatment in terms of ORR and DoR | ORR according to RECIST 1.1 as assessed by the Investigator |
| | DoR according to RECIST 1.1 as assessed by the Investigator |
| To assess the efficacy of durvalumab (MEDI4736) treatment in terms of lung cancer mortality | Lung cancer mortality |

| OBJECTIVE | ENDPOINT/VARIABLE |
|---|--|
| Secondary safety objective | |
| To further assess the safety and tolerability profile of durvalumab (MEDI4736) treatment, including all AEs | AEs, SAEs, AESIs, imAEs, physical examinations, vital signs including BP, pulse, temperature, and respiratory rate; ECGs, and laboratory findings including clinical chemistry, haematology and urinalysis |
| EXPLORATORY OBJECTIVES | |
| CCI [REDACTED] | CCI [REDACTED] |
| CCI [REDACTED] | CCI [REDACTED] |
| CCI [REDACTED] | CCI [REDACTED] |
| CCI [REDACTED] | CCI [REDACTED] |
| CCI [REDACTED] | CCI [REDACTED] |
| CCI [REDACTED] | CCI [REDACTED] |

a. TRAEs and PRAEs are used interchangeably and PRAEs will be reported in the SAP, Tables, Figures, and Listings, and CSR.

Note: Toxicities will be classified as per CTCAE grading system NCI CTCAE version 4.03. Analysis of ORR and DoR will be based upon Investigator assessment according to RECIST 1.1. Prior irradiated lesions may be considered measurable and selected as TLs providing they fulfil the other criteria for measurability.

Note: An AESI is an AE of scientific and medical interest specific to understanding of the IP. AESIs for durvalumab (MEDI4736) include, but are not limited to, events with a potential inflammatory or immune-mediated mechanism and which may require more frequent monitoring and/or interventions such as steroids, immunosuppressants and/or hormone replacement therapy. Please refer to Section 8.3.12 for AESI definition.

Note: An imAE is defined as an AESI that is associated with drug exposure and is consistent with an immune-mediated mechanism of action and where there is no clear alternate etiology.

AE: Adverse event; AESI: Adverse event of special interest; BP: Blood pressure; CSR: Clinical study report; CCI
CCI DoR: Duration of response; CTCAE: Common
Terminology Criteria for Adverse Event; ECG: Electrocardiogram; CCI
CCI
imAE: Immune-mediated adverse event; IP: Investigational
product; NCI: National Cancer Institute; ORR: Objective response rate; OS: Overall survival; OS12, OS24, OS36: Proportion
of patients alive at 12 months, 24 months, 36 months, respectively, from first date of treatment; CCI
CCI PFS: Progression-free survival; CCI
CCI; RECIST 1.1: Response Evaluation Criteria in Solid Tumours version 1.1; PFS: Progression-free
survival; PFS12, PFS24: Proportion of patients progression-free at 12 months and 24 months, respectively, from first date of
treatment; PRAE: Possibly related adverse event; SAE: Serious adverse event; SAP: Statistical analysis plan; TL: Target
lesion; CCI; TRAE: Treatment-related adverse event; CCI
CCI

Data of the following exploratory endpoints will be reported in the clinical study report
(CSR): CCI
CCI

4 STUDY DESIGN

4.1 Overall design

This is a Phase II, open-label, multi-centre study to determine safety of a fixed dose of durvalumab (MEDI4736) (1500 mg) monotherapy in patients with unresectable Stage III NSCLC who have not progressed following definitive, platinum-based sCRT.

An overview of the study design and the study flow chart are presented in [Figure 1](#) and [Figure 2](#), respectively. Details on study objectives and efficacy and safety endpoints are provided in [Table 3](#).

Number of patients and patient population

Up to 150 patients will be treated with the study drug in Europe and North America. Patients will be in complete response (CR), partial response (PR), or have stable disease (SD) following definitive, platinum-based sCRT, as assessed by the Investigator and further supported by the screening imaging radiological assessment. Patients must not have progressed following definitive, platinum-based sCRT; radiation therapy must be completed within 42 days prior to first IP dose administration. The last dose of radiation therapy is defined as the day of the last radiation treatment session.

Patients must have histologically- or cytologically-documented NSCLC and locally-advanced, unresectable Stage III disease (according to the International Association for the Study of Lung Cancer [IASLC] Staging Manual Version 8 [[IASLC 2016](#)]).

Patients will be treated with the study drug in 2 cohorts: approximately 100-120 patients in the WHO/ECOG PS 0 to 1 Cohort and up to 30 patients in the WHO/ECOG PS 2 Cohort.

Investigational product, dosage and mode of administration

Durvalumab (MEDI4736) 1500 mg via IV infusion q4w, starting on Week 1 after confirmation of eligibility, for a maximum of 24 months from Cycle 1 Day 1, or until PD (unless the Investigator considers the patient continues to receive benefit from the IP), initiation of alternative cancer therapy, unacceptable toxicity, withdrawal of consent, or another discontinuation criterion is met.

Treatment initiation within the first 14 days after sCRT therapy is, however, highly encouraged. For patients who are recovering from toxicities associated with prior treatment, administration of the first IP dose may be delayed by up to 42 days from the end of the sCRT.

For details on treatments given during the study, see Section 6.1.

Tumour response assessments

Tumour assessments using CT/MRI will be performed at the times specified in Table 1 and Table 2. RECIST 1.1 measurements as assessed by the Investigator will be used to derive the secondary variables of PFS, ORR, and DoR. Categorisation of objective tumour response assessment will be based on the RECIST 1.1 criteria of response: CR, PR, SD and PD.

Overall survival assessments

Once a patient has had objective progression recorded and has discontinued study drug, the patient will be followed up for survival status q12w until death, withdrawal of consent or the end of the study.

Schedule of assessments

The SoA at screening and during the treatment period is presented in Table 1. The SoA during follow-up for patients who have discontinued the study drug due to confirmed PD, toxicity, or any other reason, is presented in Table 2.

Guidelines for the management of toxicities are described in Section 8.4.5.

Details of the PGx component of the study (relating to deoxyribonucleic acid [DNA]) are provided in Appendix D.

Interim analysis

No formal interim analysis is planned for this study. However, the SC will conduct an early safety evaluation when 10 patients in the WHO/ECOG PS 2 cohort have been treated for a minimum of 6 months or discontinued due to an AE or disease progression, whichever occurs first. At the time of the early safety evaluation, safety data for patients in the WHO/ECOG PS 0 to 1 cohort will also be provided to the SC for completeness in the overall risk/benefit assessment. If needed for publication purposes, an additional early assessment of study data

[figure not shown]
may be conducted when minimum 50 patients in the WHO/ECOG PS 0 to 1 cohort or WHO/ECOG PS 2 cohort have had the opportunity to receive durvalumab (MEDI4736) for a minimum of 6 months.

End of analysis portion of study

Once the planned statistical analyses have been performed, the analysis portion of the clinical study will have been completed. Patients in OS follow-up (progressed and have completed treatment) will be considered to have completed the study.

For patients who continue to receive IP after the time of the data cut-off (DCO), Investigators will report all SAEs to AstraZeneca Patient Safety until 90 days after last IP dose. Following the DCO for the study, SAE reporting applies only to patients who are receiving IP or who are within the 90-day follow-up period post the last dose of IP (for more details see Section 4.4).

Figure 2 Study flow chart

- ^a Screening assessments can be performed in a step-wise process. The baseline tumour assessment is part of the screening procedures and should be performed within 42 days after the end of sCRT and 28 days before the start of study drug. For patients who are recovering from toxicities associated with prior treatment, IP treatment initiation may be delayed by up to 42 days from the end of the sCRT.
- ^b During the treatment period, patients who are clinically stable at an initial RECIST 1.1-defined radiological PD may continue to receive study drug at the discretion of the Investigator and patient. A follow-up scan is to be performed after the initial RECIST 1.1-defined radiological PD, no less than 4 weeks after the prior assessment of PD and no later than the next regularly scheduled imaging visit, and this scan is evaluated using the Confirmation of Radiological Progression Criteria outlined in [Appendix F](#). If the subsequent scan does not confirm the immediate prior radiological PD, then the patient may continue on study drug at the discretion of the Investigator and if the patient has consented to do so; imaging assessments should continue until the next RECIST 1.1-defined radiological PD, which in turn will require a subsequent scan evaluated using the Confirmation of Radiological Progression Criteria outlined in [Appendix F](#). For all patients who are treated through progression, the Investigator should ensure patients do not have any significant, unacceptable, or irreversible toxicities that indicate continuing treatment will not further benefit the patient. The patient must continue to meet those inclusion and exclusion criteria that are relevant to treatment through disease progression as specified in [Section 6.1.3](#). Patients with rapid tumour progression or with symptomatic progression that requires urgent medical intervention (eg, central nervous system metastasis, respiratory failure due to tumour compression, spinal cord compression) will not be eligible to continue to receive study drug.
- ^c Patients with confirmed PD who continue to receive the study drug at the discretion of the Investigator (following consultation with AstraZeneca) can receive the study drug for a maximum of 24 months from Cycle 1 Day 1. For all patients who are treated through progression, the Investigator should ensure patients do not have any significant, unacceptable, or irreversible toxicities that indicate continuing treatment will not further benefit the patient. The patient must continue to meet those inclusion and exclusion criteria that are relevant to treatment through disease progression as specified in [Section 6.1.3](#). The same exceptions as noted in footnote ^b apply. Patients will follow the assessments in [Table 1](#) including tumour assessments q8w (relative to the date of IP treatment initiation) until the study drug is stopped. Patients who continue to receive treatment after the DCO should receive tumour assessment scans and other assessments as per local clinical practice. It is recommended that the patients continue the scheduled site visits and Investigators monitor the patient's safety laboratory assessments prior to and periodically during the treatment with durvalumab (MEDI4736) in order to manage AEs in accordance with the durvalumab (MEDI4736) toxicity management guidelines ([Section 8.4.5](#)). The study drug should be discontinued if there is confirmed PD in TLs following a previous response (PR or CR) to the study drug in those lesions.

Note: At DCO for the study, patients who are receiving IP can either choose to discontinue from the study or, where the Investigator judges that patients are gaining clinical benefit, patients may continue to receive IP. For patients who do continue to receive IP beyond the time of the DCO, Investigators must continue to report all SAEs to AstraZeneca Patient Safety until 90 days after last IP dose. Any SAE or non-serious AE ongoing at the time of the DCO is to be followed up at the discretion of the Investigator and per local practice and in alignment with the Dosing Modification and Toxicity Management Guidelines ([Section 8.4.5](#)), unless the event is considered by the Investigator to be unlikely to resolve or the patient is lost to follow-up.

AE: Adverse event; C: Cycle; CR: Complete response; DCO: Data cut-off; IP: Investigational product; PD: Progression of disease; PR: Partial response; SAE: Serious adverse event; q8w, q12w: Every 8, 12 weeks, respectively; RECIST 1.1: Response Evaluation Criteria in Solid Tumours version 1.1; sCRT: Sequential chemoradiation therapy; WHO/ECOG PS: World Health Organisation/Eastern Cooperative Oncology Group Performance Status; TL: Target lesion.

4.1.1 Study Conduct Mitigation During Study Disruptions Due to Cases of Civil Crisis, Natural Disaster, or Public Health Crisis

The guidance given below supersedes instructions provided elsewhere in this CSP and should be implemented only during cases of civil crisis, natural disaster or public health crisis (eg, during quarantines and resulting site closures, regional travel restrictions and considerations if site personnel or study patients become infected with severe acute respiratory syndrome coronavirus 2 [SARS-CoV-2] or similar pandemic infection), which would prevent the conduct of study-related activities at study sites, thereby compromising the study site staff or the patient's ability to conduct the study. The investigator or designee should contact the study sponsor to discuss whether the mitigation plans below should be implemented.

To ensure continuity of the clinical study during a civil crisis, natural disaster, or public health crisis, changes may be implemented to ensure the safety of study patients, maintain compliance with Good Clinical Practice (GCP), and minimize risks to study integrity. Where allowable by local health authorities, ethics committees, health care provider guidelines (eg, hospital policies) or local government, these changes may include the following options:

- Obtaining consent/reconsent (note, in the case of verbal consent/reconsent, the ICF should be signed at the patient's next contact with the study site).
- Home or Remote visit: Performed by a site qualified health care professional (HCP) or HCP provided by a third-party vendor (TPV).
- Telemedicine visit: Remote contact with the patients using telecommunications technology including phone calls, virtual or video visits, and mobile health devices.

For further details on study conduct during civil crisis, natural disaster, or public health crisis, refer to [Appendix H](#).

4.2 Scientific rationale for study design

4.2.1 Rationale for study safety endpoints

This study is designed to further evaluate the safety of durvalumab (MEDI4736) monotherapy, using a fixed-dosing regimen, in unresectable Stage III NSCLC patients who have not progressed following definitive, platinum-based sCRT. This study is designed to complement and expand the safety database from the ongoing Phase III PACIFIC Study. As the PACIFIC Study evaluated a weight-based dosing regimen (mg/kg) for durvalumab (MEDI4736), expanding data on the safety profile of the fixed-dose combination is warranted, particularly for more severe AEs, and in the context of the very recent concept of immune checkpoint blockade as consolidation therapy in unresectable Stage III NSCLC patients who have undergone sCRT. Given the potential for radiotherapy to increase the likelihood of anti-PD-L1-mediated pneumonitis, a need for additional safety data on the use of durvalumab (MEDI4736) under this context exists, including in the sub-populations of WHO/ECOG PS 0 to 1 and 2 patients, who have not been representatively included in pivotal studies.

In the PACIFIC Study, the majority of imAEs with durvalumab (MEDI4736) occurred during the first 6 months of treatment (see the current version of the durvalumab [MEDI4736] IB). This timing is consistent with published literature using anti-PD-1 or anti-CTLA-4 agents, which indicates that most of the imAEs occur within 3 to 6 months of the initiation of treatment ([Topalian et al 2014](#), [Weber et al 2017](#)). The PACIFIC 6 Study will assess the safety of durvalumab (MEDI4736) within the first 6 months of treatment as defined by Grade 3 and Grade 4 TRAEs, including the evaluation of the nature of toxicities (SAEs, AEs, AESIs, imAEs), interventions and treatment, and outcome of treatment.

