4.2.4 Rationale for treatment duration

Treatment in this study will continue up to 24 months or until RECIST 1.1-defined PD and Investigator determination that the patient is no longer benefitting from treatment with IP, or until another discontinuation criterion is met (see Section 7.1). This guidance is supported by data from the CheckMate-153 Study that indicated that patients treated with nivolumab (an anti-PD-1 agent) until PD showed superior PFS when compared to treatment with nivolumab with a 1-year fixed duration (HR: 0.43; 95% CI: 0.25, 0.76), a trend toward improved OS, and no new safety signals after 1 year of treatment (Spigel et al 2017). In the PACIFIC Study, although patients were treated for up to 12 months with durvalumab (MEDI4736), no new safety signals were observed after 6 months of treatment. Numerous Phase 3 studies are currently evaluating durvalumab (MEDI4736) treatment until PD for patients with a variety of malignancies; while the results of these studies are not yet available, no new safety signals have been identified as a result of the longer duration. The 12-month and 18-month PFS rates following durvalumab (MEDI4736) treatment in Stage III NSCLC patients in the PACIFIC Study were 55.9% (95% CI: 51.0, 60.4) and 44.2% (95% CI: 37.7, 50.5), respectively, suggesting that a significant number of patients had to discontinue therapy prior to disease progression based on the 12-month treatment regimen. Based on these observations, no new safety signals are expected beyond 1 year of treatment with durvalumab, but there exists the potential for additional clinical and survival benefit beyond 1 year of treatment. In order to balance the patient burden associated with monthly visits until disease progression with the potential for additional clinical benefit with prolonged treatment duration, durvalumab (MEDI4736) will be administered for a maximum of 24 months in this study.

4.2.5 Timing of treatment with durvalumab (MEDI4736) relative to sequential chemoradiation therapy

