### 3.2.1 Primary Safety Endpoint

The primary endpoint of this study is the incidence of Grade 3 and Grade 4 TRAEs (see Section 3.2.3.1) which occur within the first six months (ie, up to and including the 183rd day) after the initiation of durvalumab. Any Grade 3 or Grade 4 TRAEs which started after the 183rd day of the study, or after the 90th day following discontinuation of durvalumab, or after the start of subsequent anti-cancer therapy will not be included. In the tables, listings and figures, the TRAEs are presented as “possibly related adverse events” as per the CRF and AZ standards.

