### **4.3 Analysis of Primary Safety Endpoint**

The primary endpoint of this study is the incidence of Grade 3 and Grade 4 TRAEs (see Section [3.2.3.1](#)) which occur within the first six months (ie, up to and including the 183rd day) after the initiation of durvalumab. Any Grade 3 or Grade 4 TRAEs which started after the 183rd day of the study, or after the 90th day following discontinuation of durvalumab, or after the start of

subsequent anti-cancer therapy will not be included.

The number and percentage (and exact Clopper-Pearson 95% CI) of patients with NCI CTCAE Grade 3 or Grade 4 TRAEs, both overall and for those occurring within the first six months after initiation, will be summarized for the SAF for all patients and within the WHO/ECOG PS 0/1 and PS 2 groups. This summary will also be graphically presented as a bar chart. The number and percentages of patients with NCI CTCAE Grade 3 or Grade 4 TRAEs will also be summarized by SOC and PT.

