### **4.5 Analysis of Secondary Safety Endpoints**

#### **4.5.1 Adverse Events**

All AEs reported up until 90 days following completion or discontinuation of durvalumab treatment or until the initiation of the first subsequent therapy (whichever occurs first) will be included in the summaries unless explicitly stated otherwise below.

All AEs will be summarised descriptively, in terms of number of patients (n) and percentage of patients (%) reporting the event by MedDRA SOC and PT.

Listings of AEs will include the date of onset, date of resolution (if AE is resolved) and investigator's assessment of severity, relationship to durvalumab, and NCI CTCAE Grade. Separate listings will be produced for all AEs, TRAEs, SAEs, AESIs, imAEs, AEs with outcome of death, AEs leading to discontinuation of durvalumab, AEs leading to discontinuation of study. Listings of AESIs and imAEs will also include the additional information (eg, intervention, dose, duration of therapy etc.) recorded for these AEs. All AEs that are not treatment-emergent will be flagged in the data listings and the time of onset will be flagged as 'pre-treatment', 'post-treatment and no other anti-cancer therapy' and 'after initiation of other anti-cancer therapy'.

An overall summary of AE data will be presented including the number and percentage of patients reporting the following:

- At least one AE

- At least one TRAE
- At least one AE of CTCAE Grade 3 or Grade 4
- At least one TRAE of CTCAE Grade 3 or Grade 4
- At least one SAE
- At least one Serious TRAE
- At least one AE leading to discontinuation of study treatment
- At least one TRAE leading to discontinuation of study treatment
- At least one AE leading to treatment interruption
- At least one TRAE leading to treatment interruption
- At least one AE with outcome of death
- At least one TRAE with outcome of death
- At least one AESI
- At least one TRAE of special interest (AESI)
- At least one imAE (and exact Clopper-Pearson 95% CI)
- At least one immune-mediated TRAEs

The following summaries including the number and percent of patients by SOC and PT will be presented separately:

- All AEs / TRAEs
- All AEs / TRAEs of CTCAE Grade 3 or Grade 4
- All TRAEs of CTCAE Grade 3 or Grade 4 occurring within the six months of first dosed date
- All TRAEs which starts within 90 days after last dose of durvalumab (irrespective of start of subsequent anti-cancer therapy)
- All AEs

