#### **4.5.1.1 Adverse Events of Special Interest and Immune-Mediated Adverse Events**

The following summaries of AESIs will be presented by AESI category and PT:

- All AESIs / TRAEs of special interest
- All serious AESIs
- All AESIs by maximum CTCAE Grade
- All AESIs by outcome
- All AESIs leading to treatment interruption
- All AESIs leading to treatment discontinuation
- All AESIs / TRAEs of special interest with fatal outcome
- All AESIs which required treatment
- All AESIs which required treatment with systemic steroids, and high dose steroids
- All AESIs which required treatment with immunosuppressants
- All AESIs which required treatment with endocrine therapy

Overall summaries will present the numbers and percentages of patients with at least one immune-mediated AE (imAE) by the following categories:

- AEs / TRAEs,
- AEs / TRAEs of CTCAE Grade 3 or Grade 4
- SAEs / Serious TRAEs
- AEs / TRAEs with outcome of death
- AEs which required treatment
- AEs which required treatment with systemic steroids, and high dose steroids
- AEs which required treatment with immunosuppressants
- AEs which required treatment with endocrine therapy
- AEs leading to treatment discontinuation
- AEs by outcome

Using the same categories above similar summaries will be presented by preferred term, and by SOC and PT.

Time to event analyses for immune-mediated AE (imAE) will be performed by AESI categories, for:

- Time to first onset of imAE
- Time to first onset of imAE of Grade 3 or 4
- Time to resolution of imAE
- Time to resolution of Grade 3 or 4

For patients with imAEs having multiple PTs within an AESI category the AEs will be collapsed to one event if the difference between end date of an imAE and subsequent start date of the next imAE is  $\leq 3$  days. The time to onset will be based upon the first PT, whereas time to resolution used for KM analysis will be based on time of the worst imAE episode from that given patient.

At the AESI grouped term level for time to resolution outputs the worst imAE is defined in the order of the following:

- imAE with worst (highest) grade first
- For more than one imAE with the same highest grade take imAE which did not resolve before imAE which did resolve
- If multiple imAE and all resolved take imAE with longest duration

Summaries for imAEs and related data will be presented by imAE category and PT:

- At least one imAE
- At least one serious imAE
- At least one imAE by outcome

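### The SAP applies its six-month window only to Grade 3/4 TRAE counts, so SAE, AESI and imAE percentages by PS cohort depend on time on drug

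*Protocol*

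**What the plan says.** Protocol 4.2.1 states that the study "will assess the safety of durvalumab (MEDI4736) within the first 6 months of treatment as defined by Grade 3 and Grade 4 TRAEs", and continues "including the evaluation of the nature of toxicities (SAEs, AEs, AESIs, imAEs), interventions and treatment, and outcome of treatment".

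SAP 3.2.1 defines the primary endpoint as Grade 3 and 4 TRAEs "which occur within the first six months", up to and including Day 183. It leaves out events that start more than 90 days after durvalumab is stopped or after subsequent anti-cancer therapy begins. SAP 4.3 reports these TRAEs "both overall and for those occurring within the first six months after initiation, will be summarized for the SAF", with exact intervals, for all patients and by PS group. In the list of tables in SAP 4.5.1 the only six-month item is "All TRAEs of CTCAE Grade 3 or Grade 4 occurring within the six months of first dosed date".

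Other AE summaries take "All AEs reported up until 90 days following completion or discontinuation of durvalumab treatment or until the initiation of the first subsequent therapy", whichever comes first. The AESI and imAE tables in SAP 4.5.1.1, from "All AESIs / TRAEs of special interest" through those by treatment required and by outcome, state no other window. SAP 4.1.1 summarises all safety data separately by PS group. Treatment may last 24 months (SAP 1.2.1), so the whole window reaches about 27 months. SAP section 6 lists no change from protocol on this point.

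**The concern.** The protocol's rationale links the six-month assessment to serious, special-interest and immune-mediated events and to how they were treated and resolved. The planned outputs give a six-month view only of how many patients had a Grade 3/4 TRAE, and under which SOC and PT.

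For the rest, the statistic is the percentage of patients who ever had the event while on drug or within 90 days afterwards. That percentage rises with time on drug even when the risk per month is the same. The two PS cohorts will be presented separately and read against each other. A cohort that stops earlier would look safer on SAEs, AESIs and imAEs for that reason alone.

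**Working it through.** **The plan's own figures.** The Clopper-Pearson intervals in SAP 1.3 reproduce: 10/120 gives 4.1% to 14.8%, 12/100 gives 6.4% to 20.0%, and 4/30 gives 3.8% to 30.7%. They concern Grade 3/4 TRAEs. The plan gives no figure for the other safety outputs.

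**Inputs from the documents.** Maximum treatment is 24 months. The AE window runs 90 days (about 3 months) past the last dose. The six-month limit is Day 183.

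**Assumed inputs.** The first-event hazard h is 2% per month in both cohorts. Time on drug is exponential, capped at 24 months, with median m of 6 or 12 months. Subsequent therapy is ignored.

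**Constant hazard, whole window.** Let μ = ln 2 / m and s = μ + h. Then

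P = 1 − e^(−3h) × [(μ/s)(1 − e^(−24s)) + e^(−24s)].

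- m = 6: μ = 0.1155, s = 0.1355, μ/s = 0.8524, e^(−24s) = 0.0387. The bracket is 0.8581; P = 1 − 0.9418 × 0.8581 = 19.2%.
- m = 12: μ = 0.0578, s = 0.0778, μ/s = 0.7428, e^(−24s) = 0.1547. The bracket is 0.7826; P = 1 − 0.9418 × 0.7826 = 26.3%.

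**Day 183 cut.** A patient is now observed to the smaller of T + 3 and 6 months, where T is time on drug, so 24 becomes 3 in the formula.

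- m = 6: 1 − 0.9418 × 0.9507 = 10.5%.
- m = 12: 1 − 0.9418 × 0.9465 = 10.9%.

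The small remaining gap comes from patients who stop before month 3 and leave the window before month 6.

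**Hazard falling after month 6 to k × h.** With s' = μ + kh,

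P = 1 − e^(−3h)(μ/s)(1 − e^(−3s)) − e^(−6h) e^(−3μ) [(μ/s')(1 − e^(−21s')) + e^(−21s')].

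| Hazard after month 6 | Median 6 months | Median 12 months | Gap (points) |
|---|---|---|---|
| Unchanged | 19.2% | 26.3% | 7.1 |
| Halved | 15.1% | 19.2% | 4.1 |
| Quartered | 12.9% | 15.2% | 2.3 |
| Any of these, Day 183 cut | 10.5% | 10.9% | 0.4 |

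**A wider contrast.** A simulation used medians of 4 and 12 months and six-month risks of 12% and 24.2%. These are PACIFIC's Grade 3/4 TRAE and imAE percentages, borrowed only as levels. The whole-window gap ran from 16.1 − 12.3 = 3.8 points (12%, late hazard quartered) to 48.4 − 31.1 = 17.3 points (24.2%, constant hazard). With the Day 183 cut it was 11.6 − 10.8 = 0.8 and 23.3 − 21.8 = 1.5 points.

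**The exposure-adjusted rate.** SAP 4.5.1 plans a rate per 100 patient-years, for all AEs by PT only. Its numerator takes events to 90 days after the last dose. Its denominator is actual exposure, which SAP 3.2.8 ends 27 days after the last dose and which does not stop at the first event. In the constant-hazard example, mean time on drug is (1 − e^(−24μ))/μ = 8.12 and 12.98 months. Ignoring the 27 days, the rates are 19.2/(8.12/12) = 28.4 and 26.3/(12.98/12) = 24.3. The order of the cohorts reverses at equal risk. Crediting the 27 days shrinks this but leaves 63 days of event follow-up without exposure.

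**The case against.** The strongest reply is that the SAP follows the protocol's operative text. Protocol Table 3 and section 9.2 attach six months only to Grade 3/4 TRAEs. The secondary safety objective covers all AEs with no window, and 9.5.2.1 combines data from all cycles. Section 4.2.1 is rationale, and its list can be read as describing only the Grade 3/4 TRAEs. This stands. A reader might infer that the protocol promised six-month tables of every SAE, AESI and imAE and that the SAP broke the promise. The documents do not support that; the tension lies partly inside the protocol. Even on the narrow reading, though, no six-month table shows which of those TRAEs were serious, of special interest or immune-mediated, how they were treated, or how they resolved.

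The second reply is that other outputs help. Exposure and cycles are summarised, listings carry onset dates, and time to first imAE onset is planned by AESI category. The 4.3 summary gives Grade 3/4 TRAEs both overall and within six months, so later first events follow by subtraction. These soften the point but do not cover SAEs or AESIs as groups, and the patient-year rate has the limits shown above.

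The third reply is that a constant hazard to month 27 fits badly with 4.2.1, which says most imAEs in PACIFIC fell in the first six months. That is fair, and for such events the smaller gaps in the table are more apt. No hypothesis is tested, and with at most 30 PS 2 patients the interval at 4/30 is already about ±13.5 points.

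A reader might also infer that the plan needs a Day 365 cut, either to match PACIFIC's treatment of up to 12 months or to test the statement in protocol 4.2.4 that "no new safety signals are expected beyond 1 year of treatment with durvalumab". The documents do not support that. No section calls for such a cut, and the protocol quotes PACIFIC's AE percentages without their collection window. The 4.2.4 statement concerns new kinds of event, which SOC/PT tables and dated listings can show.

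**Conclusion.** The mismatch is real but modest. Under the SAP, SAE, AESI and imAE percentages by PS cohort mix risk with time on drug, and no planned output gives the six-month picture that 4.2.1 describes. At equal risk, the direction follows from the window definition: shorter time on drug gives lower percentages. The size does not follow from the documents, which give no time on drug by cohort and do not say which cohort will stop sooner. With medians of 6 and 12 months and 2% per month, the gap is about 7 points under a constant hazard and roughly 2 to 4 points if the hazard falls after month 6. With a Day 183 cut it is 0.4 points. The primary endpoint is unaffected. This is a cheap improvement to the secondary safety outputs and does not show an invalid analysis.

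**What to change.** In SAP 4.5.1 and 4.5.1.1, add the overall AE summary and the main SAE, AESI and imAE tables, including treatment required and outcome, for events with onset up to and including Day 183. Use the window rule of SAP 3.2.1 and keep the SAF as denominator, overall and by PS cohort. Keep the whole-period tables. Also reconcile protocol 4.2.1 with Table 3 and 9.5.2.1, so that it is clear whether the six-month assessment extends beyond Grade 3/4 TRAE counts.

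The cost is SAP wording, a protocol clarification and a modest number of repeat tables run with a date filter. Onset dates are already collected (protocol 8.3.4), so no new data are needed. Limiting the repeats to the main tables matters, because 4.5.1.1 already lists many AESI and imAE outputs.
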